LTHT	Leeds Teaching Hospitals Trust

Abbreviation	Term
MHRA	Medicines And Healthcare Products Regulatory Agency
MRI	Magnetic Resonance Imaging
MTX	Methotrexate
NIMP	Non-Investigational Medicinal Product
OD	Once Daily
PI	Principal Investigator
PIS	Patient Information Sheet
PK/PD	Pharmacokinetic/ Pharmacodynamic
PO	[per os] Oral Administration
QA	Quality Assurance
QoL	Quality of Life
RA	Rheumatoid Arthritis
RCT	Randomised Controlled Trial
RDMS	Research Data Management System
REC	Research Ethics Committee
RF	Rheumatoid Factor
SAE	Serious Adverse Event
SC	Subcutaneous
SD	Standard Deviation
SDAI	Simplified Disease Activity Index
SJC	Swollen Joint Count
SPC	Summary Of Product Characteristics
SSZ	Sulfasalazine
SUSAR	Suspected Unexpected Serious Adverse Reaction
T2T	Treat to target
TJC	Tender Joint Count
TNF	Tumour Necrosis Factor
U&E	Urea and Electrolytes
VAS	Visual Analogue Scale

PROTOCOL SYNOPSIS

GENERAL INFORMATION	
Short Title	TEEMS: Targeted treatment Early with Etanercept (biosimilar) plus Methotrexate or methotrexate with T2T care for DMARD-naïve early RA patients - Rationalising treatment based on naïve CD4⁺ T-cell Stratification.
Full Title	Targeted treatment early with etanercept (biosimilar) plus methotrexate or methotrexate with T2T care for DMARD-naïve early RA patients. A prospective, longitudinal cohort study with an embedded pilot randomised controlled trial to assess treatment rationalisation based on naïve CD4 ⁺ T-cell stratification.
Sponsor	University of Leeds
Sponsor ID	RR16/209
EudraCT No.	2016-002344-16
MREC No.	17/YH/0155
Chief Investigator	[name]
Co-ordinating Centre	Chapel Allerton Hospital, Leeds
National / International	National
TRIAL INFORMATION	
Phase	IV
Indication	Early rheumatoid arthritis, remission, targeted treatment
Design	Single centre, phase IV, open-label, prospective, longitudinal cohort study with an embedded pilot randomised controlled trial
Number of sites	1
Primary Objective	
• To determine whether the proportion of patients achieving clinical remission after first-line treatment with methotrexate and T2T care differs according to naïve CD4⁺ T-cell frequency (normal/abnormal) at baseline (Arm A vs. Arm B)

Secondary Objective(s)	
• To determine the proportion of patients that achieve clinical remission for patients with abnormal baseline naïve CD4⁺ T-cell frequencies receiving etanercept + methotrexate (Arm C) to obtain preliminary proof-of-concept of superior response compared to methotrexate with T2T care (Arm B)• To determine whether the proportion of patients that achieve imaging remission after first-line treatment with methotrexate differs according to naïve CD4⁺ T-cell frequency (normal/abnormal) at baseline (Arm A vs. Arm B)• To determine the values of patient-reported outcomes (EMS, VAS scales, HAQ-DI) for patients with abnormal baseline naïve CD4⁺ T-cell frequencies receiving etanercept + methotrexate (Arm C) to obtain preliminary proof-of-concept of superior response compared to methotrexate with T2T care (Arm B).• To determine whether patient-reported outcomes (, VAS scales, HAQ-DI) after first-line treatment with methotrexate differ according to naïve CD4⁺ T-cell frequency (normal/abnormal) at baseline (Arm A vs. Arm B)• To determine the proportion of patients that achieve imaging remission for patients with abnormal baseline naïve CD4⁺ T-cell frequencies receiving etanercept + methotrexate (Arm C) to obtain preliminary proof-of-concept of superior response compared to methotrexate with T2T care (Arm B)• To determine the proportion of patients who normalize their T-cell status for patients with abnormal baseline naïve CD4⁺ T-cells receiving methotrexate with T2T care or etanercept + methotrexate (Arm B & Arm C)• To determine whether the proportion of patients achieving sustained clinical remission differs between study arms• To determine whether the cumulative amount of corticosteroid use differs between study arms
Primary Endpoint(s)	
• The difference in the proportions of patients in clinical remission (DAS28ESR ≤2.6) at 24 weeks of first-line methotrexate with T2T care between those with normal (Arm A) vs. abnormal (Arm B) naïve CD4⁺ T-cell frequencies

Secondary Endpoint(s)	
• The difference in the proportions of patients in clinical remission (DAS28ESR ≤ 2.6) after 12 weeks of first-line methotrexate with T2T care between those with normal (Arm A) vs. abnormal (Arm B) naïve CD4$^{+}$ T-cell frequencies• The difference in the proportions of patients in clinical remission (DAS28ESR ≤ 2.6) at 12 weeks and 24 weeks for patients with abnormal baseline naïve CD4$^{+}$ T-cell frequencies receiving methotrexate with T2T care (Arm B) vs. etanercept + methotrexate (Arm C)• The differences in the medians of patient-reported outcome measures (EMS, VAS scales, HAQ-DI) after 12 weeks & 24 weeks of first-line methotrexate with T2T care between those with normal (Arm A) vs. abnormal (Arm B) naïve CD4$^{+}$ T-cell frequencies• The differences in the medians of patient-reported outcome measures (EMS, VAS scales, HAQ-DI) after 12 weeks & 24 weeks for patients with abnormal baseline naïve CD4$^{+}$ T-cell frequencies receiving methotrexate with T2T care (Arm B) vs. etanercept + methotrexate (Arm C)• The difference in the proportions of patients in imaging remission (PD=0) after 24 weeks of first-line methotrexate with T2T care between those with normal (Arm A) or abnormal (Arm B) naïve CD4$^{+}$ T-cell frequencies• The difference in the proportions of patients in imaging remission (PD = 0) at 24 weeks for patients with abnormal baseline naïve CD4$^{+}$ T-cell frequencies receiving methotrexate with T2T care (Arm B) vs. etanercept + methotrexate (Arm C)• The difference in the proportion of patients with normal naïve CD4$^{+}$ T-cells at 24 weeks for patients with abnormal baseline naïve CD4$^{+}$ T-cells receiving methotrexate with T2T care (Arm B) vs. etanercept + methotrexate (Arm C)• The difference in the proportions of patients achieving sustained clinical remission (DAS28ESR ≤ 2.6 at both 12 and 24 weeks) (Arm A vs. Arm B and Arm B vs. Arm C)• The difference in the average (median) cumulative amount of corticosteroid use at 24 weeks between study arms (Arm
-----------------------	---

	A vs. Arm B and Arm B vs. Arm C). This will include any administered at the 24 week visit.
TRIAL TIMELINES	
Start date	February 2020
Subject enrolment phase	54 months recruitment period (extended from 36 months)
Follow-up duration	24 weeks
End of Trial Definition	When the last patient has completed 24 weeks of follow-up of the trial and any safety data are resolved, procedures are signed off and all analyses of laboratory samples are complete.
Expected completion date	July 2025 (approx.)
TRIAL SUBJECT INFORMATION	
Number of trial subjects	16-30 to be randomised 1:1 to arm B or C, 44-46 to receive standard care in arm A (depending on recruitment rate): total 76-106.
Age group of trial subjects	18 years and older
Inclusion criteria	
• Subject has a diagnosis of RA as defined by the new ACR/EULAR 2010 classification criteria• Newly diagnosed (within 12 weeks)• Active disease at screening (DAS28ESR ≥ 3.2 or clinical evidence of synovitis i.e. at least one swollen joint)• Anti-citrullinated protein antibody (ACPA) positive• Male & female subjects ≥ 18 years old• DMARD (disease modifying anti-rheumatic drug) naïve• No use of intra-muscular, intra-articular or oral corticosteroids 4 weeks prior to screening• All male and female subjects biologically capable of having children must agree to use a reliable method of contraception for the duration of the study and 24 weeks after the end of the study period. Acceptable methods of contraception are surgical sterilisation, oral, implantable or injectable hormonal methods, intrauterine devices or barrier contraceptives.

	
• Patients must have the capacity and be willing to provide written informed consent and comply with the requirements of the protocol• Subjects should be deemed to be in good health with respect to clinical examination and screening blood tests, including full blood count (FBC), urea and electrolytes (U&E), and liver functions tests (LFT) – see exclusion criteria for further details
Exclusion criteria	
• Use of any additional investigational medications or products within 4 weeks of screening (including prior to screening)• Use of intra-muscular/intra-articular or oral corticosteroids within 4 weeks prior to screening• Use of more than one NSAID, or increase in dose of NSAIDs within 24 hours before the screening visit.• Live vaccine within <4 weeks prior to screening• Pregnant/lactating women or planning pregnancy within 24 weeks of last protocol treatment• Planned surgery within the study period (requiring omission of study medication > 4 weeks)• The presence of other comorbidities, which the physician deems as significant to interfere with evaluation (musculoskeletal condition such as osteoarthritis & fibromyalgia)• Diagnosis of another inflammatory arthritis or connective tissue disease (e.g. psoriatic arthritis or Ankylosing spondylitis, primary Sjögren's syndrome, systemic sclerosis, systemic lupus erythematosus, polymyositis)• Concomitant severe infection requiring intravenous 4 weeks prior to screening• Any contraindication to conventional DMARD's/anti-TNF therapy• Patients with abnormal liver function at the time of screening or abnormal blood tests as shown by: 
○ Aminotransferase (AST) / alanine aminotransferase (ALT) > 3x upper limit of normal (ULN) OR Bilirubin

	
> 50μmol/L
 
○ Serum Creatinine > 175 umol/L○ eGFR below 30ml/L/min/1.73m²○ neutrophils < 2000 x 10⁶/L^[1] [SEP]○ Platelets < 125 x 10⁹/L^[1] [SEP]○ Haemoglobin < 90 g/L for males and < 85 g/L for females
INVESTIGATIONAL MEDICINAL PRODUCT	
IMP name(s)	Benepali® (Etanercept biosimilar)
IMP mode of administration	Subcutaneous injection as per licenced use (solution for injection in pre-filled pen)
Duration of IMP Treatment	24 weeks
IMP Supplier(s)	Samsung Bioepis
Non IMP name(s)	
● Methotrexate (MTX)● Hydroxychloroquine (HCQ)● Sulfasalazine (SSZ)● Folic Acid (FA)● Intra-muscular/Intra-articular methylprednisolone (Depo-Medrone) or triamcinolone (Kenalog)● Oral prednisolone

1. INTRODUCTION

- Rheumatoid arthritis (RA) is a chronic inflammatory disease which, if untreated can lead to significant disability and poor quality of life (QoL).
- Treatment with disease modifying anti-rheumatic drugs (DMARD's), including biologic therapies significantly improves outcomes.
- The current aim of treatment in RA is remission and the current optimal treatment approach is to start methotrexate (MTX) therapy early.
- Different medications for RA have shown varying success in inducing and maintaining remission.
- Biologic medications are expensive and may be associated with potential serious side effects and high costs. Furthermore, long-term outcomes are unknown.
- Our previous research has demonstrated that T-cell phenotyping at baseline could predict remission in DMARD-naïve early RA patients treated with MTX.
- Prediction of MTX therapy response remains a key clinical need to enable the identification of patients who would benefit from an alternative, more aggressive treatment strategy.

This study aims to assess the clinical utility of T-cell stratification for rationalising treatment with MTX, therefore enabling early targeted treatment for those with a poorer prognosis based on their immunological status.

1.1. Background

RA is a chronic systemic autoimmune disease characterised by a symmetrical inflammatory polyarthropathy. Inflammation of the synovial lining (synovitis) is responsible for triggering structural joint damage which, if untreated can lead to significant physical disability and reduced quality of life (QoL)[1, 2]. The Incidence of RA is approximately 0.5-1% with 5-50 per 100000 adults in developed countries[3].

As there is no known cure for RA, the key therapeutic target is to suppress inflammation and prevent any deterioration in joint damage and function, thus achieving a state of remission[4]. The approach to treating RA has witnessed dramatic changes over recent years. With the advent biologic therapies and treat to target strategies, rates of clinical remission have significantly improved, making it an achievable goal[2, 5]. The European League Against Rheumatism (EULAR) has stated it as their primary treatment goal[6].

The current optimal therapeutic approach in early RA is to start MTX to target inflammation and induce remission[7]. Prediction of MTX therapy response remains a key clinical need to enable the identification of patients who would benefit from an alternative, more aggressive treatment strategy. Multiple predictors of remission with MTX have been reported over the years[8-15], reviewed in[2], but none have entered routine clinical practice.

We previously reported that T-cell phenotyping at baseline could predict remission in DMARD-naïve early RA treated with MTX. Reduced naïve T-cell frequency was the most predictive factor, using both a pilot[16] and a replication cohort (Ponchel 2015, submitted). Sensitivity/specificity at 79%/81% and a positive predictive value (PPV)/negative predictive value (NPV) at 78%/81% were reported with an odd ration of 15 for the achievement of remission (submitted). Despite small patient numbers in both the original study (n=50) and in the replication set (n=70), these data confirmed the potential value of using naïve CD4+ T-cell as a biomarker of MTX induced remission in early RA. The clinical utility of measuring T-cell subsets is therefore strongly indicated by these data and suggests that measurement of T-cell subsets can rationalise the use of MTX as first-line therapy.

In our pilot study, the association between lower naïve T-cells and the inability to achieve remission was not observed in patients treated with combination therapy MTX + anti-TNF[16]. It may therefore be appropriate to consider biologics early in patients with poor prognostic naïve CD4+ T-cells. The current proposal aims to confirm the clinical value of T-cell subset quantification for the prediction of MTX response in early RA, by stratified interventions based on naïve CD4+ T-cell status.

1.2 Investigational medicinal product (IMP)

Within the trial, the following is classed as an Investigational Medicinal Product (IMP):

- ***Benepali®:***

- Etanercept biosimilar
- Administered subcutaneously (sc) 50mg/week
- In combination with MTX is indicated for the treatment of moderate to severe active RA in adults when the response to disease-modifying anti-rheumatic drugs, including MTX (unless contraindicated), has been inadequate
- Can be given as monotherapy in case of intolerance to MTX or when continued treatment with MTX is inappropriate
- Also indicated in the treatment of severe, active and progressive RA in adults not previously treated with MTX
- Has been shown to reduce the rate of progression of joint damage as measured by X-ray and to improve physical function (alone or in combination with MTX)[17]

1.2.1. Summary of product characteristics (SPC)

- The SPC for Benepali® will be used in this study.

1.2.2. Non IMP(s)

1.2.2.1. Conventional DMARDs

- ***MTX:***

- Licenced in RA, often as first-line therapy.

- ***Hydroxychloroquine (HCQ):***

- Licenced in RA, often a second-line therapy. Can be used in combination with MTX and Sulfasalazine or monotherapy for mild disease.

- ***Sulfasalazine (SSZ):***

- Licenced in RA, often a second-line therapy. Can be used in combination with MTX and HCQ or monotherapy for patients intolerant to MTX.

1.2.2.2 Supportive medication

Folic Acid: Patients taking MTX will be co-prescribed oral folic acid as per standard care in our T2T clinic (5mg daily, 6 days per week, except day of MTX).

Administration of IMP' & non-IMPs:

- For patients with normal baseline naïve CD4⁺ T-cells (Arm A), MTX will be administered as per standard T2T care at a starting dose of 15mg/week PO*. If tolerated, dose escalation will occur at follow-up in line with our T2T schedule.
- Patients with abnormal baseline naïve CD4⁺ T-cells will be randomized to receive either MTX 15mg/week PO* (Arm B) or MTX 15mg/week PO* + Benepali® 50mg SC injection, as per licenced use (Arm C). Follow-up of patients in both arms and dose escalation of MTX will also occur in line with our T2T schedule.
- The treating physician will have been monitoring patients for side effects from the beginning of their treatment. Side effects will be monitored by clinical assessment and by blood testing at each study visit.

**(or SC as per standard practice – see section 7.3 for further guidance)*

Rescue medication/treatment of flare

- Patients in either study arm may receive corticosteroid treatment (IM/IA or oral) at any of the follow-up study visits or at unscheduled visits if they have evidence of clinical flare i.e. do not meet target DAS28ESR<2.6. Administered doses will be in line with local standard clinical practice. For patients meeting the target DAS score, however have evidence of flare i.e. synovitis as per the assessing physician, corticosteroids may be offered. Administration of this will be logged in the CRF.
- Small doses of corticosteroids are relatively safe, with only a small risk of side effects e.g. weight gain, mood and sleep disturbance, which are usually only short-lived.
- Long-term use of high doses is often associated with bone loss and worsening of osteoporosis. Rarely avascular necrosis can occur. Corticosteroids can also transiently cause an increase in blood sugars, necessitating increased blood sugar monitoring/extra caution in diabetic patients. Menstrual disturbance has also been noted.
- Injections can occasionally cause thinning of the skin or depigmentation at the injection site. Intra-articular injections may be associated with increased pain within the joint for 24 hours and rarely joint infection in less than 1:5000 cases. The need for rescue medication will be recorded as an adverse event.

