10.4. Exemptions from safety reporting

10.4.1. Efficacy endpoints and disease progression events

All events that are unequivocally due to progression of moderate to severe rheumatoid arthritis or lack of response should not be reported as an AE or SAE. This type of information will be captured in the study assessments.

Disease progression would include: increased joint pain, musculoskeletal pain, generalized body aches, uncontrolled RA, joint swelling, increased stiffness, limited motion, synoviorthesis (in or out of the hospital), and hospitalizations for RA-related procedures (joint replacement surgery, joint arthroscopy, synovectomy).

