10.5. Recording and reporting of AEs

10.5.1. Recording and reporting of all AEs

Determination of AEs should be based on the signs or symptoms detected during the physical examination and on clinical evaluation of the subject, and should be assessed and recorded at every visit. Signs and symptoms must be recorded using standard medical terminology. Subjects considered incapable of giving consent would not be considered for this study.

AEs and SAEs will be collected from the signing of the informed consent form until the last follow up visit. The Investigator must instruct the subject to report AEs and SAEs during this time period.

During the time period specified above, the Investigator will:

- Record all AEs and SAEs on source documents.
- Record all AEs and SAEs in the CRF for subjects who are not screen failures.

The Investigator must follow up on all AEs and SAEs until the events have subsided, returned to baseline, or, in case of permanent impairment, until the condition has stabilized, within the duration of the trial for each participant. There will be no follow up of AE's past the last follow up visit for each participant.

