## 11.7 Safety analyses

### 11.7.1 Adverse events

Adverse events for this trial will be summarised descriptively using the safety set. The number of serious and non-serious adverse events over the 24-week follow-up period, as well as the number and percentage of participants these events occurred in, and the exposure by 100 patient-years will be reported for each trial group.

The number of serious adverse events in each trial group will be broken down by reason for classification as serious adverse event and relationship of event to treatment and outcome. The number of non-serious adverse events in each trial group will also be broken down by relationship of non-serious adverse event to treatment and outcome.

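### Two protocol rules conflict on whether a steroid-treated flare is an adverse event, so the SAP's adverse event counts by arm may take in lack of efficacy

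*Protocol*

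**What the plan says.** **Protocol 1.2.2.2 (rescue medication/treatment of flare).** Patients may receive corticosteroids at follow-up or unscheduled visits "if they have evidence of clinical flare i.e. do not meet target DAS28ESR<2.6". There is a second route for patients who meet the target but have "evidence of flare i.e. synovitis as per the assessing physician, corticosteroids may be offered". The subsection closes with an unqualified rule: "The need for rescue medication will be recorded as an adverse event".

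**Protocol 10.4.1 (exemptions from safety reporting).** Events that are unequivocally due to progression of RA "or lack of response should not be reported as an AE or SAE". The examples of progression include "increased joint pain, musculoskeletal pain, generalized body aches, uncontrolled RA, joint swelling, increased stiffness, limited motion". As to where these events go instead: "This type of information will be captured in the study assessments".

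**Protocol 10.5.1.** The investigator is to "Record all AEs and SAEs in the CRF for subjects who are not screen failures". Whatever is classed as an adverse event therefore reaches the dataset.

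**SAP 11.7.1.** The safety summary gives "The number of serious and non-serious adverse events over the 24-week follow-up period", the participants affected and an exposure-based figure per 100 patient-years, for each trial group. It has no rule for flare or rescue entries.

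**Steroid use elsewhere.** SAP 7.2.6 takes steroid name, dose and type from the Concomitant Medications CRF and builds the cumulative corticosteroid outcome from them.

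**The concern.** The main trigger for rescue is an efficacy criterion, failure to reach the DAS28ESR target. Recording rescue as an adverse event therefore turns an efficacy failure into a safety entry, and 10.4.1 appears designed to prevent that. Staff following one section would log the event; staff following the other would not.

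The trial is planned on the expectation that remission differs between arms. If flare entries reach the adverse event data, their number will follow remission, and the arm with less remission will show more adverse events even where the treatments are equally safe. Clinicians know both treatment and T-cell result (Protocol 6.5.4), so the two rules could also be applied differently by arm.

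**Working it through.** The plan states no figure on this point, so the check has two parts: a comparison of the rules, then an illustration of size.

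**1. Do the rules cover the same event?** Take a patient whose RA responds inadequately, who misses the DAS28ESR target with swollen joints, and who receives a steroid.
- Under Protocol 1.2.2.2, an adverse event is recorded. No exception is given.
- Under Protocol 10.4.1, if the flare is unequivocally lack of response, it is not reported as an adverse event and is left to the study assessments.
- Protocol 7.5.1 treats new steroid use as an intervention to be recorded and does not call it an adverse event.
- Protocol 9.4.6, on unscheduled visits including those for flare, calls for side effects related to the IMP to be recorded as adverse events. It does not say that the flare or the steroid is one.
- No section ranks these rules, and the SAP amendment log shows no change on the point.

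The overlap is real and unresolved.

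**2. How large could the effect be at Week 24, Arm A against Arm B?**

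Inputs from Protocol 12.9 and SAP 9: planning remission of 68% with normal and 25% with abnormal T-cell frequency, and minimum arm sizes of 44 (A) and 16 (B). Non-remission is therefore 1 − 0.68 = 0.32 in Arm A and 1 − 0.25 = 0.75 in Arm B.

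Assumptions: one entry per patient; 24 weeks of exposure for everyone, i.e. 168 / 365.25 = 0.46 years; non-remission treated as off target (remission is ≤2.6 and the target is <2.6, so they differ only at exactly 2.6). Let f be the share of non-remitters who receive rescue and have it logged. The documents do not give f, so it is varied from 0 to 1.

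Formulas: share with an entry = (1 − remission) × f; rate per 100 patient-years = 100 × share / 0.46.

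| f | Arm A | Arm B | Gap (points) | Per 100 patient-years, A vs B |
|---|---|---|---|---|
| 1 | 32% (about 14 of 44) | 75% (12 of 16) | 43 | 70 vs 163 |
| 0.5 | 16% (about 7 of 44) | 37.5% (6 of 16) | 21.5 | 35 vs 82 |
| 0.25 | 8% | 18.75% | 10.75 | 17 vs 41 |
| 0 | 0% | 0% | 0 | 0 vs 0 |

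The f = 0 row also describes a trial in which 10.4.1 is followed throughout.

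**3. Arm C.** The text gives no planning remission rate for Arm C. The caption of the Protocol's study schematic mentions expected proportions by arm, but the figure was not in the copy used here. Only the direction can be stated: if Arm C remits more often than Arm B, the same mechanism would add more entries to Arm B.

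**The case against.** The strongest reply is that section 10 governs. It is the dedicated pharmacovigilance section, 10.4.1 is framed as an exemption, and the rescue sentence closes a bullet on steroid injection risks in the introduction. Sites could reasonably follow 10.4.1, and then nothing enters the counts. This stands as a reason to word the consequence conditionally. It does not remove the conflict, because no text gives section 10 precedence.

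A second reply is that one section speaks of recording and the other of reporting, and that the exemption covers only unequivocal cases. This narrows the overlap. However, 10.4.1 sends exempt events to the study assessments, while the SAP counts whatever is in the adverse event data. The word unequivocally also leaves the remaining flares to the judgement of unblinded clinicians.

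Third, missing the target is not the same as receiving rescue. Steroids may be given, and treat-to-target care also allows DMARD changes. This stands, and it is why f runs down to zero.

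Fourth, there is mitigation:
- SAP 11.7.1 splits events by relationship to treatment, so flares judged unrelated could be seen there, although they remain in the totals.
- Cumulative steroid use is compared by arm (SAP 11.6.9), so an imbalance in rescue would be visible.
- Protocol 12.6 tabulates SAEs only, and a steroid dose for flare is not in itself serious.
- The adverse event summaries are descriptive, and no inferential tests are planned for Arm B against Arm C.

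All of this stands and limits the importance of the point.

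**Conclusion.** The two protocol rules conflict as written, and SAP 11.7.1 has no means of separating the entries affected. The distortion is conditional: it arises if 1.2.2.2 is followed or practice is mixed, and is zero if 10.4.1 is followed throughout. Under the planning rates and the assumptions above, the Week 24 gap between Arms A and B runs from 0 to 43 percentage points as f goes from 0 to 1. It falls on descriptive, mainly non-serious adverse event tables; the primary endpoint is untouched. The sponsor should correct this, but it does not threaten the main result.

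The documents do not support two stronger readings that a reader might infer:
- **That the adverse event tables are bound to mix efficacy with safety, so that etanercept will look safer than methotrexate alone.** Nothing shows which rule sites follow, and the text gives no remission rate for Arm C.
- **That multiplying non-remission by the three follow-up visits gives an upper bound of 3 × 0.75 = 2.25 entries per patient in Arm B against 3 × 0.32 = 0.96 in Arm A.** This applies Week 24 rates to Weeks 4 and 12, and omits unscheduled visits and the second route to rescue, so it is not a ceiling. If early remission is low in every arm, it would also overstate the difference between arms.

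**What to change.** 1. Reconcile Protocol 1.2.2.2 with 10.4.1 so that one recording rule applies to RA flare and to the need for rescue steroid, and state it in both places.
2. In SAP 11.7.1, tabulate entries that consist only of RA flare or need for rescue steroid in a separate row by trial group. Present adverse event totals and rates per 100 patient-years with and without them. This works whichever rule the sponsor adopts, and also if data were already collected under mixed practice. The Concomitant Medications CRF can help to identify the entries.

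The cost is a protocol clarification and a small addition to the adverse event table. No new data collection and no change to treatment are needed.
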